## 8.2.8. Time to Complete Clearance of Baseline Warts

The time to complete clearance of baseline warts is calculated as the number of days between the date of first dose of study medication and the date that the baseline wart count is 0. Subjects who do not have clearing of baseline warts will be censored at the date of their last study assessment.

Kaplan-Meier (KM) estimates of clearance rates at Week 2, Week 4, Week 8 and Week 12 and their 95% CIs will be presented by treatment group. Vehicle Gel subjects will be separated into QD and BID groups. For estimates by week, week will be defined by the maximum day allowable by the visit windows (e.g., the summary for Week 2 will count all subjects with clearance on or before Day 18.) Because clearance is a positive outcome, clearance rates for each week will be calculated as (1 – the KM survival probability estimate). The median time to clearing and 95% CI for each treatment group will also be summarized. Inverse KM curves based on (1 – the KM survival probability estimates) will be plotted to describe the estimated proportion of subjects with clearance over time for each treatment group.

## 8.2.9. Recurrence of Baseline Warts Cleared Prior to Week 12

The time to recurrence of baseline warts which have previously cleared is calculated as the number of days between the first date that baseline wart count is 0 and the first date after that for which baseline wart count is > 0. Subjects who do not have recurrence of baseline warts after clearing will be censored at the date of their last study assessment.

Kaplan-Meier estimates and plots will be presented for the time to recurrence in a similar manner to that described above for time to clearing; however as recurrence is negative outcome, the KM curves will be based on the KM survival probability estimates. Also, as clearing can occur at any visit, the KM estimates of recurrence will be based on 14 day intervals from the date of clearing: 2 Weeks (14 days), 4 Weeks (28 days), 6 Weeks (42 days), 8 Weeks (56 days), and 10 Weeks (70 days) post clearing. KM curves will be presented for each treatment arm, with Vehicle Gel subjects separated into QD and BID groups.

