#### 4.2.1 WART COUNTS

EGW/PAW counts will be captured separately and the location of the warts marked on source documents. The baseline warts and the total wart counts will be counted at Baseline and all post-treatment visits. EGW/PAW that arise during the study will be identified, marked on source documents and reported separately for post-baseline visits.

If an EGW/PAW clears during treatment, as determined by the Investigator, the subject will discontinue study drug application for that specific EGW/PAW, but other EGW/PAW will continue to be treated. For baseline warts that clear during treatment, the Investigator will assess recurrence of treated and cleared EGW/PAW on subsequent study visits.

If all warts (those present at baseline and new warts that develop during the study) clear, as determined by the Investigator, the subject will not continue to apply study drug and will remain in the study for all scheduled post-baseline assessments to assess for wart recurrence.

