### 4.4.2. Visit Windows

By-visit analyses will be performed using the reported CRF visit. The one exception is the Week 12/ET visit. For safety endpoints that are not measured at every visit (e.g. lab values and vital signs), the Week 12/ET will be mapped to Week 12 but presented in tables/listings as Week 12/ET. For all other endpoints, for subjects who complete the study, the Week 12/ET visit will be mapped to "Week 12" and used in by visit analyses. For subjects who are early terminations, the Week 12/ET visit will be mapped to "ET" (early term and will not be included in the by visit analyses. The ET visit may be used for LOCF of missing data. The ET visit will be carried forward only to visits for which the ET visit occurred prior to on the last study day of the analysis visit window using the following windows:

Analysis Visit	Visit Window (Based on Study Day)
Week 2	Day 2 to Day 22
Week 4	Day 23 to Day 45
Week 8	Day 46 to Day 71
Week 12	Day 72 +

Table 1: Analysis	Visit	Windows
-------------------	-------	---------

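### SAP 8.2.8 dates clearance and censoring by actual visit, so the order of Week 12 visit dates can lift the Kaplan-Meier clearance estimate above the proportion cleared and produce an unsupported median

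*SAP*

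**What the plan says.** SAP 8.2.8 measures time to clearance from the date of first dose to the date the baseline wart count is 0. For everyone else: "Subjects who do not have clearing of baseline warts will be censored at the date of their last study assessment". Clearance rates at Weeks 2, 4, 8 and 12 are one minus the Kaplan-Meier (KM) estimate, read at the end of each visit window: "For estimates by week, week will be defined by the maximum day allowable by the visit windows". The SAP's example is that "the summary for Week 2 will count all subjects with clearance on or before Day 18". It adds "The median time to clearing and 95% CI for each treatment group will also be summarized" and a plot of 1-KM "to describe the estimated proportion of subjects with clearance over time for each treatment group". No between-arm test is specified.

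Wart counts are taken only at scheduled visits and at early termination (ET). Protocol Table 4 allows ±3 days at Week 2 and ±5 days at Weeks 4, 8 and 12. Under Protocol 4.2.1, a subject whose warts all clear "will remain in the study for all scheduled post-baseline assessments to assess for wart recurrence".

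SAP 4.4.2 says "By-visit analyses will be performed using the reported CRF visit". That rule covers by-visit analyses, not the KM analysis. We found nothing in the SAP that puts completers on a common Week 12 date, uses nominal visit times, or specifies an interval-censored method.

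SAP 8.2.9 applies the same kind of rule to recurrence: "Subjects who do not have recurrence of baseline warts after clearing will be censored at the date of their last study assessment". It reads KM at exact 14-day multiples from clearing.

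**The concern.** KM treats a censored subject as someone whose later status is unknown and passes that subject's weight to events seen afterwards. That is right for a dropout. It is wrong for a non-cleared completer seen on day 79 when another completer is found clear on day 86. Both had all four scheduled assessments and differ only in when the last one was booked. Subjects who cleared earlier and keep attending do not correct this, because their event is already counted.

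The report would then carry two Week 12 clearance figures for the same arm, the 1-KM estimate and the crude proportion, that differ because of visit scheduling. A median time to clearing could also be printed for an arm in which most subjects never cleared. Arms are small and vehicle is split by dosing frequency, so one clearer seen late in the window can dominate the estimate.

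**Working it through.** **Reproducing the SAP's figure.** The SAP counts first dose as Day 1. With first dose on the baseline day, the Week 2 window ends on SAP Day 14 + 3 + 1 = 18, which matches 8.2.8. By the same rule Week 12 is read at SAP Day 84 + 5 + 1 = 90. Below, days are counted from first dose, so the Week 12 window is days 79-89 and the reading point is day 89.

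**Formula.** 1-KM = 1 - Π(1 - d/r), where d is the number of clearers on a day and r the number still at risk, with events before censoring at ties.

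**Worked example (hypothetical), n = 22, no dropout, all visits in window.** Four subjects clear on day 56. Two first clear at Week 12, on days 82 and 86. The 16 non-clearers are seen on days 79, 80, 80, 81, 82, 82, 83, 84, 84, 85, 86, 86, 87, 88, 88, 89.
- Day 56: r = 22, d = 4.
- Day 82: r = 22 - 4 - 4 censored earlier = 14, d = 1.
- Day 86: r = 22 - 5 - 10 censored earlier = 7, d = 1.
- Crude: 6/22 = 27.3%.
- 1-KM: 1 - (18/22)(13/14)(6/7) = 34.9%.

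Moving single visits:

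| Change | Week 12 1-KM |
|---|---|
| Second clearer on day 89, the day-89 non-clearer on day 88 (r = 1) | 100% |
| Second clearer on day 89, that non-clearer also on day 89 (r = 2) | 1 - (18/22)(13/14)(1/2) = 62% |
| Second clearer on day 92, after the window | 1 - (18/22)(13/14) = 24.0%, below crude; the plotted tail then reaches 100% |

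In the first two rows the survival estimate drops from (18/22)(13/14) = 0.76 to below 0.5 on day 89, so a median is printed although 27.3% cleared.

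**Limit on the median shift.** KM cannot depart from the observed curve until someone is censored. The earliest in-window Week 12 censoring is day 79, so the first event that can be inflated is on day 80. The latest in-window observed median is day 89. The largest shift is 89 - 80 = 9 days.

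**Typical size.** The documents give no clearance rates, clearance timing or visit spread, so these are assumptions. Four equal cohorts of 120/4 = 30 at 3:1 give about 22 per active arm and about 8 in the twice-daily vehicle group. The simulation used n = 22, true clearance 30%, no dropout and visit days uniform in the windows. One fifth to one half of clearers first cleared at Week 12, the rest split 1:2 between Weeks 4 and 8 (3,000 arms per case).

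| Week 12 visits | Mean 1-KM | Median gap from crude | KM below crude |
|---|---|---|---|
| All within ±5 days | 39-50% | 3-15 points | 0% of arms |
| All within ±1 day | 35-40% | 2-9 points | not reported |
| 10% fall 1-7 days late | 35-41% | 2-8 points | 8-10% |
| 20% fall 1-7 days late | 32-35% | 1-4 points | 17-26% |

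In the first row, 3-8% of arms print 100%, and 19-42% of arms with under half cleared still print a median. At true clearance of 10% with one fifth of clearers at Week 12, 76% of arms have a gap under 2 points. Week 8 readings matched the crude proportion in every run.

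**Dropout check.** With 20% dropout assumed, mean 1-KM on actual dates is 0.40-0.49; on nominal visit times it is 0.30, the true value.

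**The case against.** Last-assessment censoring is a standard convention. The effect sits inside one visit window of a descriptive, untested secondary endpoint in a study that SAP 4.1 says is not powered for efficacy. Every magnitude rests on assumed clearance rates, timing, visit spread and arm size, and at low clearance most arms barely move. A median called too early is early only against visit-dated times; against the unobserved true clearance date, visit dating makes times late. All of this stands, and it limits how much weight the point can carry. It does not remove the mechanism, which follows from the estimator.

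A reader might infer more than the documents support:
- *That KM always overstates clearance.* It does not. It equals the crude proportion if nobody first clears at Week 12 or if all Week 12 visits fall on one in-window day. With late visits it can fall below.
- *That the efficacy conclusions are compromised.* The primary proportion (8.1.1) and the by-visit proportions (8.2.3 to 8.2.5) do not use these dates. The interim outputs (SAP Table 2) contain no time-to-clearance table.
- *That a repaired KM must equal the primary proportion.* The primary counts missing as not cleared, whereas KM censors. With 20% dropout assumed, the nominal version still averages about 4-5 points above crude. That difference is by design.
- *That recurrence estimates in 8.2.9 are wrong by a known amount.* The 10-30% recurrence in Protocol 1.1 describes current treatments and has no time horizon, so there is no target to measure against.

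**Conclusion.** The point holds for the completer artefact in 8.2.8. With no dropout and all Week 12 visits in window, Week 12 1-KM is at or above the crude proportion cleared, whatever the clearance rate. The median may be up to 9 days earlier than the visit-dated observed median, or be printed without half the arm clearing. Once some Week 12 visits fall after the window, the direction is not guaranteed in a given arm.

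Confidence is high in the mechanism and direction, and limited in the size: the 39-50% against a true 30% is conditional on the assumptions listed in the working. Because the endpoint is descriptive and secondary, this should be fixed before the tables are produced, but it does not threaten the main analysis.

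In 8.2.9 the supportable remark is narrower. On-schedule Week 8 visits (days 51-61) and Week 12 visits (days 79-89) may be 79 - 61 = 18 to 89 - 51 = 38 days apart, so the exact 28-day reading can miss on-schedule recurrences.

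**What to change.** In 8.2.8, use the nominal scheduled visit (Weeks 2, 4, 8, 12) as event and censoring time for scheduled assessments. Place all completers' Week 12 assessments at nominal Week 12 whatever their date, with events before censoring at ties. An ET clearance keeps its actual date and must never be dated at or before a visit with a documented non-zero baseline wart count. If the last such visit was early enough that its nominal day falls on or after the ET date, place the ET clearance just after that nominal day.

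With no dropout this gives cleared/N at Week 12, including when visits are late (27.3% in every variant of the worked example). With dropout it removes the visit-order artefact but not the designed difference from the missing-as-not-cleared proportion.

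A smaller alternative keeps actual dates, censors non-cleared completers at SAP Day 90 (or their actual date if later), and ends the plot and the median at Day 90. It also gives cleared/N with no dropout and in-window visits, but it leaves out clearers seen after Day 90: the day-92 variant reads 1 - (18/22)(17/18) = 22.7%.

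In 8.2.9, add a note that scheduled visit spacing can exceed the 28-day reading point.

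The cost is SAP wording and a small derivation change, with no new data. Week 12 KM figures will usually be lower, though they can rise in arms with late visits.

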### 1.5 SUMMARY OF BENEFITS AND RISKS

External warts (EGW) and perianal warts (PAW) are sexually transmitted diseases caused by infection with papillomaviruses. In the Shope Cottontail rabbit animal model, topical application of NVN1000 Gel inhibited growth of wild type and mutant papillomavirus (Coggan, 2014).

Nitric oxide released from NVN1000 is anticipated to be pharmacologically active in the skin with no systemic exposure to NVN1000 or nitric oxide. In a 5-day cross-over pharmacokinetic study in adults with moderate to severe acne in which NVN1000 Gel at a final concentration of 8% (SB204) was applied to 17% BSA, there was no systemic exposure to NVN1000 and no difference in serum nitrate levels following repeated topical administration.

Dermal toxicology studies have demonstrated minimal evidence of toxicity in a 13-week miniature pig study, low dermal irritation in rabbits, and no dermal sensitization in guinea pigs. Local application site events in a 13-week dermal toxicology study in rats led to premature discontinuation of all dose groups in a time-dependent manner. These local adverse effects seen in the rat study are species specific and monitorable. Tolerability will be assessed during the planned study, and discontinuation criteria for intolerance by subjects is described in Section 6.7.

The independent DSMB will monitor safety and tolerability.

Topical application has been associated with local application-site reactions including erythema, peeling, scaling, or burning/stinging. These local application-site reactions may occur due to the active agent (NVN1000) or the vehicle. Local application-site events including erosions and contact dermatitis were reported in subjects with psoriasis treated with NVN1000 Gel and Vehicle Gel under occlusion and in two subjects in the first cohort dosed in this study with NVN1000 Gel 8% or Vehicle Gel. Within 2 weeks of dosing, these subjects developed severe erythema, burning or erosions leading to treatment discontinuation. At the time of this protocol amendment, it is unknown which treatment these subjects received.

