# 4.1.7 DISCONTINUATION/WITHDRAWAL PROCEDURES

A subject may voluntarily withdraw from study participation at any time, for any reason. If the subject withdraws consent and discontinues from the study, the Investigator will attempt to determine the reason for discontinuation and record the reason in the subject's study records and in the study database. If a subject is withdrawn because of an AE, that AE should be indicated as the reason for withdrawal. In the event of early discontinuation, (i.e., prior to Week 12/Day 84 visit) and whenever possible, the subject should be asked to return to the study center to complete the Week 12/ET evaluations. Subjects who withdraw from the study will not be replaced.

If at any time during the study the Investigator determines that it is not in the best interest of the subject to continue, the subject will be discontinued from participation. The Investigator can discontinue a subject at any time if medically necessary. The Investigator may discontinue a subject's participation if the subject has failed to follow study procedures or to keep follow-up appointments. Appropriate documentation in the subject's study record and the study database regarding the reason for discontinuation must be completed.

All subjects who fail to return to the study center for the Week 12/ET visit will be contacted by telephone to determine the reason(s) why the subject failed to return for the necessary visit or elected to discontinue from the study. If a subject is unreachable by telephone after a minimum of

two documented attempts (one attempt on two different days), a certified letter will be sent requesting that the subject contact the Investigator.

Reasons for an Investigator's withdrawal of a subject may include, but are not limited to, the following:

- Safety (e.g., severe adverse reactions, pregnancy);
- Lack of efficacy as determined by the Investigator;
- When the requirements of the protocol are not adhered to (e.g., significant issues with dosing compliance);
- When a concomitant medication or treatment likely to interfere with the results of the study is reported, or required, by the subject (the Investigator will decide, in consultation with PPD, whether the subject is to be withdrawn);

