### 6.7 DISCONTINUATION OF INDIVIDUAL SUBJECTS FROM THE STUDY

Subjects who develop intolerance to the product as defined by scores of 'severe' (3) on 2 or more categories of tolerability (erythema, edema, erosions/ulcers, burning/stinging) shall be discontinued from the study.

Subjects with a confirmed methemoglobin > 5.0% at any post-baseline visit will be discontinued from the study. A confirmed methemoglobin is defined as at least 2 readings within 0.5% of each other taken within a 30 minutes period.

If a subject is determined to be pregnant prior to Week 12, the subject will be discontinued from the study but followed until term.

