#### 8.1. Primary Efficacy Endpoint

## 8.1.1. Proportion of Subjects with Complete Clearance of Baseline EGW/PAW at or Before Week 12

The primary efficacy endpoint is the proportion of subjects with complete clearance of baseline EGW/PAW at or before Week 12.

The number and proportion of subjects with complete clearance of baseline warts will be summarized by treatment group and each active dose group will be compared to vehicle using pairwise Pearson's chi-square tests. The Mantel-Haenszel odds ratios and corresponding 95% confidence interval (CI) will be presented. The Vehicle Gel arm will be separated into once-daily (QD) and twice-daily (BID) groups and compared pairwise to the corresponding active treatments. The three once-daily active treatment groups (8%, 16%, and 24%) will be compared to the Vehicle Gel QD group and the NVN1000 8% BID group will be compared to the Vehicle Gel BID group. The pairwise comparisons will be computed without concern for controlling for multiplicity. The primary analysis will be performed for the ITT population.

Percentages will be calculated based on the number of subjects in the ITT analysis population. Subjects who have clearance of baseline warts at or before the Week 12 visit will be counted as cleared for the analysis. Subjects who do not have a documented clearance by the end of study, including subjects with missing data at the Week 12 or other assessments, will be considered not cleared for the analysis.

The primary analysis will be repeated for the PP population. Subgroup analysis for gender and wart location (EGW/PAW) will also be performed for the ITT population. The subgroup summaries will be descriptive only with no statistical hypothesis testing performed.

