# 8.2.1. Proportion of Subjects with Complete Clearance of Total EGW/PAW at or Before Week 12.

The number and proportion of subjects with complete clearance of total EGW/PAW will be summarized by treatment group and each active dose group will be compared to its corresponding vehicle group using pairwise Pearson's chi-square tests. The Mantel-Haenszel odds ratios and corresponding 95% CI will be presented.

Subjects who have clearance of baseline warts at or before the Week 12 visit will be counted as cleared for the analysis. Subjects who do not have a documented clearance by the end of study, including subjects with missing data at the Week 12 or other assessments, will be considered not cleared for the analysis.

Subgroup analysis for gender and wart location (EGW/PAW) will also be performed for the ITT populations. The subgroup summaries will be descriptive only with no statistical hypothesis testing performed.

# 8.2.2. Proportion of Subjects with Complete or Partial Clearance of Baseline EGW/PAW at or Before Week 12

The number and proportion of subjects with complete or partial clearance, defined as a reduction in the number of baseline EGW/PAW, will be summarized by treatment group and each active dose group will be compared to its corresponding vehicle group using pairwise Pearson's chi-square tests. The Mantel-Haenszel odds ratios and corresponding 95% CI will be presented.

Subjects who have clearance, complete or partial, of baseline warts at or before the Week 12 visit will be counted as cleared or partially cleared for the analysis. Subjects who do not have a documented clearance or partial clearance by the end of study, including subjects with missing data at the Week 12 or other assessments, will be considered not cleared or partially cleared for the analysis.

## 8.2.3. Proportion of Subjects with Complete Clearance of baseline EGW/PAW at Weeks 2, 4, 8, and 12

The number and proportion of subjects with complete clearance of baseline EGW/PAW at each post-baseline visit will be summarized by treatment group and each active dose group will be compared to its corresponding vehicle group using pairwise Pearson's chi-square tests. The Mantel-Haenszel odds ratios and corresponding 95% CI will be presented.

Imputation of missing data will be performed using a last-observation carried forward (LOCF) method where a missing assessment is replaced by the previous visit's assessment.

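### Censoring every uncleared subject at the actual last assessment means that 1 − KM in SAP 8.2.8 can equal or exceed the primary clearance proportion but not fall below it, even with no dropout

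*SAP*

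**What the plan says.** SAP 8.2.8 measures time from first dose to the date the baseline wart count is zero. Its censoring rule is "Subjects who do not have clearing of baseline warts will be censored at the date of their last study assessment", with no distinction by reason for leaving and none between leavers and completers. It continues: "clearance rates for each week will be calculated as (1 – the KM survival probability estimate". The week is read at the last day the visit window allows, with Day 18 given as the Week 2 example. The inverse curves are plotted "to describe the estimated proportion of subjects with clearance over time for each treatment group". The section specifies no test and no competing-event or sensitivity analysis.

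Two other SAP analyses cover complete clearance of baseline warts:

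- SAP 8.1.1 (primary): subjects with no documented clearance, "including subjects with missing data at the Week 12 or other assessments, will be considered not cleared for the analysis".
- SAP 8.2.3 (by visit): last observation carried forward, "where a missing assessment is replaced by the previous visit's assessment". A subject who leaves uncleared therefore stays uncleared.

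On leaving, Protocol 6.7 says that subjects scored severe in two or more tolerability categories "shall be discontinued from the study". Protocol 4.1.7 gives as a possible reason for withdrawal by the investigator: "Lack of efficacy as determined by the Investigator". Protocol 1.5 reports two Cohort 1 subjects who, within two weeks of dosing, "developed severe erythema, burning or erosions leading to treatment discontinuation"; their treatment was not known when the amendment was written.

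**The concern.** A 1 − KM curve can be read as the proportion of subjects cleared only if those censored would have gone on to clear at the same rate as those still observed. That is doubtful for someone withdrawn for lack of efficacy, and it is untestable for someone removed for intolerance, because no later wart counts exist.

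Of the three clearance analyses, only 8.2.8 takes uncleared leavers out of the denominator, and nothing in the SAP reconciles it with the other two. One report could then carry two different rates for the same event by Week 12. If exits differ between arms, the excess differs between arms, and the curves may show a gap that the counts do not.

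The rule also acts on completers. Week 12 visits may fall on any of 11 days, but the estimate is read at the end of the window. A completer found uncleared early in the window is censored before another subject's clearance later in the same window, although both have had their Week 12 assessment.

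**Working it through.** **Landmark day.** The only figure in the plan to reproduce is Day 18 for Week 2. Target day + window + 1, with first dose as Day 1, gives 14 + 3 + 1 = 18, which agrees. The same rule gives 84 + 5 + 1 = Day 90 for Week 12.

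**Inputs.** About 120 subjects, 3:1, four cohorts (SAP 3.1 and 4.1). Equal cohorts of 30 are an assumption and give 30 × 0.75 = 22.5, so about 22 active subjects per cohort. The documents state no clearance or dropout rate. All rates and dates below are assumptions.

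**Direction.** KM passes a censored subject's weight to those still at risk. If all clearances fall by the landmark day, 1 − KM is therefore at least cleared/n. It is larger whenever an uncleared subject is censored before a later clearance.

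**Leavers only, visits on nominal days.** If a share d leaves uncleared before the first clearance and p is the primary proportion, 1 − KM = p/(1 − d).

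| d | p = 10% | p = 20% | p = 30% |
|---|---|---|---|
| 10% | 11.1% | 22.2% | 33.3% |
| 20% | 12.5% | 25.0% | 37.5% |
| 30% | 14.3% | 28.6% | 42.9% |

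**Unequal exits.** Take two arms of 22 with 4 clearers each (18.2%), clearing 0, 1, 1, 2 at Weeks 2, 4, 8, 12.

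- Five leavers after Week 2 and one after Week 4: 1 − (16/17)(14/15)(12/14) = 24.7%.
- One leaver after Week 2: 1 − (20/21)(19/20)(17/19) = 19.0%.

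The gap is 5.7 points with identical counts.

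**Leavers and visit dates together.** Take 22 subjects. Four clear, on Days 29, 57, 85 and 88; 4 leave uncleared on Day 15; 7 completers are seen uncleared on Day 82 and 7 on Day 90. The primary proportion is 4/22 = 18.2%.

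- SAP 8.2.8: 1 − (17/18)(16/17)(8/9)(7/8) = 30.9%.
- Cumulative incidence with leaving as a competing event, actual dates: 1/22 + 1/22 + (16/22)(1/9) + (16/22)(8/9)(1/8) = 25.3%.
- Leavers held at risk, completers still censored on actual dates: 1 − (21/22)(20/21)(12/13)(11/12) = 23.1%.
- All uncleared subjects held to Day 90: 1 − (21/22)(20/21)(19/20)(18/19) = 18.2%.

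Dealing with the leavers alone does not restore agreement.

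**No dropout.** Simulate 22 subjects with 4 clearing (0, 1, 1, 2) and visit days uniform within the protocol windows. Mean 1 − KM at Day 90 is about 33% and the median about 28%, against 18.2%. About 3 to 4% of runs reach 100%, which happens when the last subject still at risk clears. With nominal visit days the excess disappears.

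**Against what leavers would have done.** Suppose stayers clear at 25% and 20% of subjects leave. 1 − KM gives 25.0% throughout. The true rate is 0.8 × 25% + 0.2 × f × 25%, where f is the leavers' clearance rate relative to stayers: 20.0% at f = 0, 22.5% at f = 0.5, 25.0% at f = 1 and 27.5% at f = 1.5.

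**The case against.** The strongest reply is that a different missing-data rule for a time-to-event summary is a choice of estimand. Time to clearance is one of nine secondary endpoints, the protocol asks only that it be summarized, no test is attached, and no KM output is among the interim tables. The clearance analyses that carry tests already count leavers as non-responders or carry their last status forward. This stands, and it limits the weight of the point.

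A reader might infer that the curve contradicts the primary endpoint. It does not. It uses a different, unreconciled rule and leaves the primary result untouched.

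A reader might also infer that 1 − KM overstates true clearance. That is certain only against the primary's rule. Against the unobserved outcomes of leavers it needs f below 1, which is plausible for lack of efficacy but not shown for intolerance. Other exits, such as loss to follow-up, may be unrelated to clearance. Treating every leaver as never clearing is also an assumption.

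Nor do the documents support a bias in favour of active treatment. Protocol 1.5 says that local reactions may come from the active agent or the vehicle.

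The plan mitigates part of the problem. Wart counts are due at early termination, so clearance at exit is captured if the subject attends, and reasons for discontinuation are tabulated by treatment group. Neither changes the curve, and neither touches the visit-date effect in completers.

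**Conclusion.** The point holds in a limited form. As specified, 8.2.8 gives a Week 12 clearance figure that can match or exceed the primary proportion but not fall below it, provided Week 12 clearances occur by Day 90. There are two separate causes: leavers removed from the risk set, and completers censored on actual visit dates within the window. The second needs no dropout.

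The size and the direction between arms cannot be determined from the documents. The illustrations run from about 1 to 13 points for 10 to 30% early dropout, and to about 15 points on average for visit-date spread alone (33% against 18.2%). They rest on assumed rates and uniformly spread visits; tighter scheduling would shrink the second figure. The affected display is secondary, descriptive and untested. It is worth correcting because the SAP presents it as the proportion of subjects cleared.

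**What to change.** Amend SAP 8.2.8 in one of two ways:

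1. Hold all uncleared subjects, leavers and completers alike, at risk as not cleared to the Week 12 window limit.
2. Assign each assessment to its nominal visit week, as SAP 4.4.2 already does by CRF visit for by-visit analyses, and report the cumulative incidence of clearance with discontinuation before clearance as a competing event.

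Either makes the Week 12 estimate match the primary proportion among dosed subjects. Under the first option, a Week 12 clearance recorded after Day 90 should be placed at the limit. The SAP should also say how a subject who was dispensed drug but never dosed is handled, since that subject is in the ITT denominator but has no start date for the clock.

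Keep the censored KM as a supportive display, labelled as assuming non-informative censoring, with leavers listed by reason and arm.

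The cost is SAP wording and a standard procedure; no new data are needed. The main curve would no longer estimate a hypothetical clearance rate without dropout, but the supportive KM would still show it.
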